7.6. Exposure to Study Drug and Compliance

Extent of exposure will be summarized for each treatment arm based on SAS. The following variables will be summarized:

- Duration of treatment (in months): $(\text{Date of the last dose} - \text{Date of the first dose} + 1) / 30.4375$
 - For subjects who are still on treatment at a data cut-off date, the data cut-off date will be the date of the last dose.
 - Duration of treatment will be summarized as a continuous as well as a discrete variable (≥ 1 month, ≥ 3 months, ≥ 6 months, ≥ 9 months, ≥ 12 months)
- Actual Dose Intensity (mg/day): $\text{Actual Total Dose} / \text{Duration of Treatment (days)}$
- Relative Dose Intensity (%): $\text{Actual Dose Intensity} / \text{Planned Dose Intensity}$, where the planned total daily dose is the dose assigned at the study entry.
- Dose modifications (dose decreased, dose held) and the reasons for dose modifications.

In addition, a separate table for placebo subjects who crossed-over and received AG-120 will be provided by using the same analysis method.

8. EFFICACY ANALYSIS

For PFS, best overall response (BOR), ORR, DOR and other endpoints based on progression and/or response status, the primary analyses will be based on the independent central review by IRC. The endpoints based on Investigator assessment will be used as secondary analyses. Efficacy data after crossover will be analyzed separately.

After unblinding at local PD per Investigator assessment, subjects on AG-120 are allowed to stay on AG-120 if the treating Investigator deems they are clinically benefiting. The IRC will read all scans up to the discontinuation of AG-120. Subjects on placebo will no longer stay on placebo after radiographic disease progression and unblinding, hence no further scans will be read by IRC beyond the initial locally assessed disease progression imaging time point. Because of that, there is a potential systematic bias that subjects on the AG-120 arm could have PD called by IRC later than the locally assessed PD date; however, subjects on the placebo arm would systematically be censored by IRC analysis at the time of local PD if not concordant with local PD. To alleviate the potential imbalance between two arms, IRC assessments after the local PD from both arms will be excluded from the primary analysis of scan-related endpoints per IRC read. A sensitivity analysis by including all the scans read by IRC will be conducted.

All efficacy analyses will be based on the ITT set unless stated otherwise. If analyses are performed on more than one analysis set, the analyses on the ITT set will be considered primary. For each period, once the PD occurred, or the new anticancer therapy was initiated, all the subsequent tumor/response assessments will not be included in the tumor/response related summary analyses, but it will be included in the data listings.

Data after crossover (such as PFS) will be analyzed in a similar manner.

Listings for all efficacy endpoints will be provided.

8.1. Progression-Free Survival (PFS)

8.1.1. Primary Analyses of PFS

The primary analysis of PFS will be based on IRC assessment for ITT set.

Progression-free survival (PFS) is defined as the time in months from the randomization date to the date of the first documentation of disease progression as determined by the IRC per RECIST v1.1 or death due to any cause, whichever occurs first.

$$\text{PFS} = (\text{Earliest Date of Disease Progression or Death} - \text{Randomization Date} + 1) / 30.4375.$$

The approach regarding handling of missing response assessments and censoring is presented in [Table 1: Handling of Missing Response Assessment and Censoring for the Primary Analysis of PFS](#).

A stratified log-rank test (one-sided) will be used to compare PFS of the AG-120 arm against the placebo arm at the time when 131 investigator-assessed events have occurred, with the one-sided significance level controlled at 0.025. The HR (AG-120/placebo) and the corresponding 2-sided 95% confidence interval (CI) will be estimated using a stratified Cox regression model. For both the stratified log-rank test and stratified Cox regression model, the strata will be those used for stratified randomization, that is, the number of prior lines of therapy at randomization.

Number of subjects with events, types of events (progression or death), and number of subjects censored, number of subjects for each reason of censoring, Kaplan-Meier estimates, and 95% CIs for the 25th percentile, median, and the 75th percentile for PFS will be presented by treatment group. Probabilities of event free at selected time points, such as 3-month, 6-month, 9-month, and 12-month, will be presented by treatment arms. Kaplan-Meier curves of PFS will be provided for each treatment arm with the number of subjects at risk over time included.

8.1.2. Additional Analyses of PFS

The following analyses of PFS will be performed by treatment arms:

For IRC assessments:

- Stratified log-rank test and Cox regression based on all scans read by IRC prior to crossover, including the scans after local PD from subjects who were originally assigned to AG-120 and continued to stay after unblinding.
- Stratified log-rank test and Cox regression based on PPS set.
- Unstratified log-rank test (one-sided) to compare the two treatment arms. An unstratified Cox regression will be used to estimate the HR (AG-120/placebo) with its 95% CI.
- Subgroup analysis with unstratified log-rank test and unstratified Cox regression model. The HR (AG-120/placebo) with its 95% CI will be displayed for all subgroups graphically in a forest plot. The subgroups will include:
 - The actual number of prior line of therapies in advanced setting (1 vs. ≥ 2)
 - Gender (female vs. male)
 - Extent of disease at screening (locally advanced vs. metastatic)
 - If subject had both local and metastatic, it would be considered as metastatic
 - Intrahepatic vs. extrahepatic
 - Perihilar will be included in extrahepatic category
 - ECOG at baseline (0 vs. ≥ 1)
 - Regions (North America vs. Europe vs. Asia)

In addition, the following exploratory analyses may be performed:

- PFS analysis by excluding subjects who progressed early (≤ 47 days within randomization date, i.e., 6 weeks + 5 days of scan visit window).
- The Cox regression model by including treatment, sum of target lesions at baseline, and other possibly related parameters in covariates.

For Investigator assessments:

- Stratified log-rank test (one-sided) will be utilized to compare the two treatment arms. A stratified Cox regression model will be used to estimate the HR (AG-120/placebo)

with its 95% CI. The same censoring rule as described for the primary PFS based on IRC assessment will be used.

In addition, the concordance of PFS between investigator and IRC assessment will also be summarized by treatment arms and overall.

Table 1: Handling of Missing Response Assessment and Censoring for the Primary Analysis of PFS

Situation	Date of Censoring
No baseline assessment and no death.	Date of the randomization
Alternate anticancer systemic treatment started before documented progression (PD) or death.	Date of last adequate assessment prior to the start of anticancer treatment ¹
No adequate post-baseline assessment and no death.	Date of the randomization
No documented PD or death before data cutoff date.	Date of last adequate assessment ¹
Documented PD or death following a long gap from the previous adequate assessment (eg, 2 or more consecutive missed scheduled disease status assessments). The long gap is defined as ≥ 95 days (ie, 12 weeks + 10 days per the protocol defined visit window). If no adequate assessment prior to minimum of (PD, death), the long gap is calculated from the randomization date.	Date of last adequate assessment prior to the first occurrence of 2 or more consecutive missing scheduled assessments

¹ Adequate disease assessment is defined as a response assessment other than “not assessed” or “not evaluable.” If there is no adequate response assessment prior to the start of anticancer treatment, it will be censored at the randomization date.

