12.7.1. Analysis for the Primary Endpoint

The primary endpoint of PFS is defined as the time from the date of randomization to the date of first documentation of disease progression as determined by the IRC per RECIST v1.1 or death due to any cause, whichever occurs first.

Subjects without documentation of disease progression or death at the time of the primary analysis of PFS will be censored at the date of the last response assessment prior to the start of alternate therapy. If disease progression or death is documented after 1 single missing response assessment, the actual event date of disease progression/death will be used for the PFS event date. If disease progression is documented after 2 or more missing response assessments, the PFS time of these subjects will be censored at the date of the last response assessment (CR or PR or SD) prior to 2 or more missing response assessments. Detailed censoring rules will be specified in the SAP.

The primary efficacy analysis will be the comparison of the distribution of PFS between the two treatment arms using a log-rank test stratified by the randomization stratification factor at one-sided 2.5% level of significance. Assuming a proportional hazard model for PFS, the null hypothesis will be tested:

$$H_{01} \text{ (null hypotheses): } \Theta_1 \geq 0 \text{ vs. } H_{a1} \text{ (alternative hypotheses): } \Theta_1 < 0$$

where Θ_1 is the log hazard ratio of PFS in the AG-120 (investigational treatment) arm vs. placebo (control) arm.

A Cox regression model stratified by the randomization stratification factor will be used to estimate the HR of PFS comparing the AG-120 arm with the placebo arm, along with the 95% CI.

Kaplan-Meier estimates of PFS, including estimates of the median and other quantiles, as well as individual time points (eg, 3-month, 6-month, and 12-month rates), will be presented for each treatment arm. Patterns of censored data will be examined between the treatment arm and placebo arm by summarizing the number of PFS events that are censored and by tabulating the reasons for censored observations.

There will be no interim analysis for PFS. The analysis of PFS will be performed when 131 Investigator-assessed PFS events have occurred, expected at approximately 32 months after the first subject is randomized in the study. The primary analysis of PFS will be based on IRC response assessments.

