4. OVERALL STUDY DESIGN

This is a Phase 3, multicenter, randomized, double-blind, placebo-controlled efficacy and safety study of orally administered AG-120 in subjects with advanced cholangiocarcinoma (nonresectable or metastatic). Subjects, all personnel involved in the evaluation of subjects' response to treatment (eg, Investigators, study coordinators, study pharmacists), and designated Sponsor team members will be blinded to study treatment until documented disease progression.

Subjects are required to have a histologically consistent diagnosis of IDH1 gene-mutated cholangiocarcinoma that is not eligible for curative resection, transplantation, or ablative therapies. Subjects must have documented progression of disease and have received treatment with at least 1 but not more than 2 prior treatment regimens for advanced disease (nonresectable or metastatic). At least 1 of the prior regimens must have included gemcitabine or 5-FU. Systemic adjuvant chemotherapy will be considered a line of treatment if there is documented disease progression during or within 6 months of completing the therapy, with Sponsor approval.

A total of approximately 186 subjects will be randomized in a 2:1 ratio to the AG-120 and placebo arms, respectively, stratified by number of prior therapies (1 vs. 2). The primary analysis of PFS will occur once 131 PFS events have been determined by Investigator assessment. Overall survival will be analyzed twice, once at the time of PFS primary analysis and once at the occurrence of 150 OS events.

Subjects who meet all study eligibility criteria will be randomly assigned in a 2:1 ratio to receive AG-120 orally at a dose of 500 mg once daily (QD) or AG-120-matched oral placebo QD. Daily study treatment will begin on C1D1. Cycles are 28 days (+/-2 days) in duration and dosing is continuous. Study visits will be conducted every other week during Cycles 1-3 (Days 1 and 15), and Day 1 of each cycle thereafter. Radiographic assessment (computed tomography [CT] or magnetic resonance imaging [MRI]) for evaluation of disease response will be conducted every 6 weeks (± 5 days) for the first 8 assessments (ie, through week 48) and every 8 weeks (± 5 days) thereafter from C1D1, independent of dose delays and/or dose interruptions, and/or at any time when progression of disease is suspected.

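### SAP Table 1's fixed 95-day gap treats one missed scan like two once scans are 8-weekly, against protocol 12.7.1 (minor, but wrong as written)

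*SAP*

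**What the plan says.** Protocol 12.7.1 counts missed assessments. After one miss: "If disease progression or death is documented after 1 single missing response assessment, the actual event date of disease progression/death will be used". After two or more, and for progression only: "If disease progression is documented after 2 or more missing response assessments, the PFS time of these subjects will be censored", with the last response assessment before the gap as the censoring date. It then leaves detailed censoring rules to the SAP.

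SAP Table 1 uses days instead. The row covers progression or death after a long gap and gives two or more consecutive missed assessments only as an example. The operative definition follows: "The long gap is defined as ≥ 95 days (ie, 12 weeks + 10 days per the protocol defined visit window". For a subject with no earlier adequate scan, "If no adequate assessment prior to minimum of (PD, death), the long gap is calculated from the randomization date". The censoring date in the same row is the "Date of last adequate assessment prior to the first occurrence of 2 or more consecutive missing scheduled assessments". Footnote 1 adds: "Adequate disease assessment is defined as a response assessment other than" not assessed or not evaluable, so one unevaluable scan has the same effect as one missed scan.

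The scan interval is not constant. SAP Section 4 plans scans "every 6 weeks (± 5 days) for the first 8 assessments (ie, through week 48) and every 8 weeks (± 5 days) thereafter", and they run "thereafter from C1D1, independent of dose delays and/or dose interruptions, and/or at any time when progression of disease is suspected". The same censoring rule is applied to Investigator PFS (SAP 8.1.2) and to DOR (SAP 8.6). SAP Section 11 lists only the pharmacokinetic analyses as a change from the protocol.

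**The concern.** Twelve weeks plus ten days is two 6-week intervals plus both visit windows. It is therefore the longest gap that one missed scan can produce while scans are 6-weekly. After week 48 one missed scan leaves a 16-week gap, so a limit meant to detect two misses is triggered by one. The protocol counts the event; the SAP's day limit censors it. This is the primary endpoint, and the difference is not declared.

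The row also conflicts with itself. Its trigger is met after one miss, but its censoring date is defined by a run of two or more. Two programmers could code it differently.

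The secondary point is the start of the gap. With no adequate post-baseline scan it runs from randomization, while scans run from C1D1. Any delay between the two uses up part of the 95 days.

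**Working it through.** Gaps are differences between dates, and each scan may be 5 days early or late, which gives 11 × 11 = 121 date pairs for two scans.

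1. **The plan's own figure.** 12 × 7 + 10 = 94, so 95 is the first day beyond it. One miss with 6-weekly scans gives 84 ± 10 = 74 to 94 days. The limit reproduces and is never reached in this phase.
2. **Last adequate scan at week 42, week 48 missed, progression at week 56.** 14 × 7 = 98, range 88 to 108. The gap is below 95 when the difference in offsets is −4 or less: 7+6+5+4+3+2+1 = 28 pairs. So 121 − 28 = 93 pairs reach 95.
3. **Last adequate scan at week 48 or later, one miss.** 16 × 7 = 112, range 102 to 122. All 121 pairs reach 95.
4. **Earliest event affected.** The earliest week-42 scan is day 294 − 5 = 289, and 289 + 95 = 384.
5. **No adequate post-baseline scan, week 6 missed, progression at week 12.** The gap from randomization is 84 + delay + offset (−5 to +5). It reaches 95 on 0 of 11 in-window dates for a delay of 0 to 5 days, 1 at 6, 2 at 7, 6 at 11 (the first delay that catches an on-schedule scan) and all 11 from 16.
6. **Rough size.** With the planning medians of 6 and 3 months (SAP Section 5) and dropout set to the planned 22%, about 10 of about 132 events fall after week 48. If 5 to 20% of these follow one missed scan (an assumption), 0.5 to 2 events are lost.
7. **Simulated size, C1D1 on the day of randomization.** Inputs from the plan: 124 and 62 subjects, 5 per month for 6 months then 8 per month, exponential PFS, 22% dropout, cutoff at month 32. Assumed: scans missed or not evaluable at random, and every event a progression found on a scheduled scan.

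| Scans missed or not evaluable | 5% | 10% | 20% |
|---|---|---|---|
| Events wrongly censored, of total | 0.8 of 125 | 1.5 of 123 | 2.3 of 115 |
| HR, 95-day rule vs count of misses | 0.503 vs 0.503 | 0.498 vs 0.499 | 0.497 vs 0.499 |
| Power (%), same comparison | 95.2 vs 95.3 | 95.3 vs 95.4 | 95.0 vs 95.4 |
| AG-120 Kaplan-Meier at day 540 | 0.138 vs 0.133 | 0.144 vs 0.134 | 0.164 vs 0.145 |

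   Power rests on 3,000 trials, so each value has a standard error of about √(0.95 × 0.05 / 3000) = 0.4 points. Of the wrongly censored events, 83% are in AG-120. At 10% missed, 1.2 of the 7.4 AG-120 events after day 384 are lost, about 1 in 6. Quartiles do not change, and the AG-120 12-month rate falls by 0.001 to 0.003.
8. **These counts are upper estimates.** If half of progressions are found on an unscheduled scan within 14 days, they fall to 0.5/0.9/1.4. Excluding IRC reads after local progression (SAP Section 8) lowers them further and is not modelled.
9. **Delay scenarios, every subject given the same delay.** Extra week-12 events lost at 5/10/20% missed: none at 0 to 5 days, 0.25/0.5/0.9 at 6, 1.6/3.0/5.4 at 11, 3.0/5.6/10.0 at 16. At 11 days the HR is 0.500 vs 0.502, 0.499 vs 0.502 and 0.491 vs 0.497. At 11 days and 10% missed, each arm's median moves up by 20 days or more in 9% of trials.

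**The case against.** **The row can be read in line with the protocol.** It mentions two or more misses, and its censoring date exists only in that case. That shows the likely intent, but the mention is an example and the next sentence defines the gap in days. What stands is that the row is ambiguous, which is itself a reason to correct it.

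**The protocol leaves detail to the SAP.** It does, but only after stating the single-miss rule outright, and reversing a stated rule is a change. The objection does stand for deaths after two or more misses. Protocol 12.7.1 is silent there, so a reader who sees Table 1's censoring of those deaths as a contradiction goes too far.

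**The delay is hypothetical.** This stands. A reader might infer that week-12 progression is censored whenever C1D1 is 6 or more days after randomization. At 6 days only the last in-window date is affected. The documents give no delay. Protocol Table 3 footnote 15 assigns the allocation at Screening, but protocol 8.4 requires eligibility to be confirmed before randomization. The SAP also counts its 38-day and 47-day scan limits (8.2 and 8.1.2) from randomization.

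**Late single misses are not always affected.** This also stands. Protocol 8.5.2 and Table 3 footnote 3 restart 6-weekly scans from the EOT Visit for subjects who stop treatment without progression. While that schedule is 6-weekly, one miss stays at 74 to 94 days.

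**The effect is too small to matter.** For the primary conclusion, yes. A reader might infer that losing late AG-120 progressions biases the result towards AG-120, but with no delay the HR moves by at most 0.002.

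**Conclusion.** The row is wrong as written, and the severity is minor. On the C1D1 schedule the 95-day limit catches most single misses across the change of interval (93 of 121 date pairs) and all of them from week 48 on, although protocol 12.7.1 counts those events. The difference is undeclared, and the row's trigger and censoring date disagree after one miss.

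With no delay between randomization and C1D1, about 1 to 2 of roughly 120 events are lost at 5 to 20% missed scans. The visible effect is confined to the AG-120 Kaplan-Meier tail beyond 12 months. The documents give no missed-scan rate, so that range is an assumption.

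The start-of-gap problem is possible, not established. It needs a delay of at least 6 days and a missed week-6 scan, and the figures by delay describe trials in which all subjects wait equally long. Nothing here puts the primary conclusion at risk. Single-miss deaths add almost nothing: 0.02 to 0.05 of the wrongly censored events if 15% of events are deaths. Deaths after two or more misses were not estimated. The effect on DOR is negligible, because it is only listed for responders.

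**What to change.** In SAP Table 1, replace the 95 days with a count of consecutive scheduled assessments that were missed or not evaluable on the subject's own scan schedule:

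- Count progression or death after a single miss on its actual date.
- Censor progression only after two or more consecutive misses, at the last adequate assessment before the first of them.
- With no adequate post-baseline scan, count scheduled scans from C1D1, or from randomization for subjects never dosed.
- Apply the same rule to Investigator PFS and DOR.
- List any remaining difference from protocol 12.7.1 in SAP Section 11, including whether deaths after two or more misses are censored.

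If a day limit is kept for scheduled scans on the C1D1 schedule, the SAP's own logic gives 95 or more days (last adequate scan at week 36 or earlier), 98 + 10 + 1 = 109 or more (week 42) and 112 + 10 + 1 = 123 or more (week 48 or later). Two misses give at least 116, 144 and 158 days respectively, so they are still caught. The limits do not fit a schedule restarted from EOT: two missed 6-weekly scans give 126 ± 10 = 116 to 136 days, and 28 of 121 date pairs fall below 123.

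Protocol 7.1 describes PFS follow-up scans without a restart from EOT, while 8.5.2 and Table 3 footnote 3 count them from EOT. These must be reconciled before either rule is programmed.

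The cost is one table row, one derivation rule, an entry in Section 11 if a difference remains, and that reconciliation. No new data are needed: randomization, C1D1, EOT and scan dates are already collected.

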8.2. Objective Response Rate (ORR)

Objective response rate will be derived from BOR. Best overall response is defined as the best time point response that a subject achieves during the course of the study, with the response ranked according to the following order (from best to worst): CR>PR>SD>PD>UNK>Other (including Not Evaluable and Not Assessed). The number and proportion of ITT subjects with each category of BOR will be presented by treatment arms.

Per RECIST v1.1, SD that occurred within <38 days from the randomization date is assigned as UNK (6 weeks minus 5 days per protocol allowed visit window). In addition, the BOR of CR or PR requires a confirmation scan. The specific confirmation rule can be found in [Appendix A: Best Overall Response Confirmation Rule](#).

The estimated ORR (percent of subjects with a BOR of CR or PR) and a 2-sided 95% CI (via exact binomial) will be provided by treatment arms. All subjects in the analysis set will be included in the denominator in the calculation of the percentage for each response category or ORR. If the subject has no response assessment, it will be treated as a non-responder in the analyses.

Objective response rate will be analyzed using one-sided Cochran-Mantel-Haenszel (CMH) test (see Appendix B: One-Sided Cochran–Mantel–Haenszel (CMH) Test) to compare the two treatment arms. The odds ratio and its 95% CI will be estimated. The strata will be those used for stratified randomization. If the number of responders in each arm is low ($n < 5$), Fisher exact test will be used instead. The odds ratio (unstratified) and its 95% exact CI will be estimated.

In addition, the ORR (and BOR) without confirmation per IRC as well as per Investigator assessments will be analyzed similarly.

The waterfall plots of the maximum % reduction from baseline in target lesion measurement (sum of diameters) will be presented by treatment arms. The target lesions post-baseline vs. baseline have to be matched in order to calculate % change, except for the case where lesions disappeared (*Absent* or *Too Small to Measure*) or merged or split. If the lesion status is “Absent,” 0 mm will be used as the measurement; if the lesion status is “too small to measure,” 5 mm will be used per RECIST v1.1 guidance.

The swim lane plot of treatment duration per subject will be presented by treatment arms. Treatment ongoing status will be marked at the end of the lane. The BOR will be marked in colors. The swim lane plot will be based on ITT set.

